2.4 Statistical Software and Quality Control

All statistical analyses will be performed using SAS® version 9.3. Tables, figures and data listings will be generated in Microsoft® Word® as well as PDF® format.

Quality control of SAS® programs will include a review of the whole process of result generation:

- Review of all analysis SAS® programs
- Review of SAS® log for errors, uninitialized variables and warnings •
- Review of all tables, listings and figures for completeness and correctness

2.5 Blinding and Randomization

This study is conducted in a double-blind manner in regard to assignment to treatment groups A, B, C or D. An assignment to the measles booster groups M1 and M2 will be apparent to both subject and study personnel, but the vaccination sequence will also be kept double-blind (the allocation to M1 or to M2 is unknown). The vaccine will be prepared by authorized personnel otherwise not involved in the conduct of the study or in the assessment of safety or efficacy after randomization.

At Visit 0, eligible subjects will be assigned to one of six treatment groups in timely order and received a three-digit randomization number using randomization envelopes provided by data management. The site will also be provided with emergency envelopes for unblinding in case of emergency and if knowledge of the treatment assignment is mandatory for emergency treatment.

2.6 Descriptive Analyses

Descriptive analyses of continuous variables (summary statistics) will be performed with the number of nonmissing observations (N), arithmetic mean, standard deviation (±SD), median, quartiles (Q1 and Q3) and range (minimum and maximum).

Categorical variables (frequency statistics) will be described with the number of non-missing observations and percentages (%). Percentages will be calculated within each stratum on the total number of non-missing observations.

2.7 Inferential Analyses

Inferential analysis on immunogenicity endpoints will only be performed on the PP and ITT population. The significance level will be 0.05. All p-values will be two-sided and rounded to four decimal places.

GMTs and GMT ratios will be estimated by applying an analysis of variance (ANOVA) by using log-10 transformed data and taking the anti-log of the resulting point estimates for the least squares means, least squares means differences and the corresponding 2-sided 95% Cls. Pairwise comparisons for multiple comparisons will be adjusted according to Tukey-Kramer. For the definition of the baseline percentiles treatment groups A, B, C and D will be used.

2.7.1 Inferential Analysis for the Primary Endpoint

The primary immunogenicity analysis will compare the PRNT₅₀ antibody geometric mean titer (GMT) on Day 56 between the treatment groups (CV1, CV2, A, B, C, D, M1, M2).

GMTs and GMT ratios will be estimated with including the factor vaccination group. GMTs for the MV-CHIK groups will be compared pairwise.

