### 6.3 Randomization

At Visit 0, eligible subjects will be assigned to one of six treatment groups in timely order and receive a three-digit randomization number using randomization envelopes provided by data management. The site will also be provided with emergency envelopes for unblinding in case of emergency and if knowledge of the treatment assignment is mandatory for emergency treatment.

Treatment groups A, B, C and D:

All subjects will receive three i.m. injections on study day 0, 28 and 196. Subjects randomly allocated to group A or B will receive either MV-CHIK low dose or a control-vaccine (Priorix® or MMR-Vax-Pro® or equal measles vaccine). Subjects randomly allocated to group C or D will receive MV-CHIK high dose or a control-vaccine. Block randomization will be used with a randomization ratio of 1:6 (control-vaccine : MV-CHIK).

All subjects of treatment groups A, B, C and D additionally will be randomized to one of two treatment sequences. Group A + C will receive vaccinations (MV-CHIK or control vaccine) on day 0 and 28 and placebo injection on day 196 whereas groups B + D receive placebo injection on day 0 and vaccinations (MV-CHIK or control vaccine) on day 28 and 196.

Measles booster group M1 and M2:

All subjects will receive five i.m. injections and the first injection on day -28 will be the control vaccine (Priorix® or MMR-Vax-Pro® or an equal measles vaccine). Subjects will be randomly allocated to receive MV-CHIK on day 0 and on 28 (and placebo on day 168 and 196), or to receive MV-CHIK on day 168 and on 196 (and placebo on day 0 and 28). Randomization ratio between the two booster groups will be M1 : M2 = 1 : 1

Randomization of 320 subjects to one of the six treatment groups:

Group A: MV-CHIK low : control-vaccine = 60 : 10

Group B: MV-CHIK low : control-vaccine = 60 : 10

Group C: MV-CHIK high : control-vaccine = 60 : 10

Group D: MV-CHIK high : control-vaccine = 60 : 10

Group M1:M2 MV-CHIK high day 0+28 : MV-CHIK high day 168+196 = 20 : 20

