### 13.4 Sample Size Justification

No formal sample size calculation has been performed for this phase 2 trial, but the sample size is typical for phase 2 trials, and in our experience, has been useful to assess the immunogenicity of vaccines.

Results of the predecessor study MV-CHIK-101 allow to assess the usefulness of the chosen sample size:

In phase I study MV-CHIK-101, a GMT of 7.3 (LOG10 SD 0.254) at day 28 in the placebo group and a GMT 13.7 (LOG10 SD 0.515) in the lowest dose group (MV-CHIK 0.05 mL = 1.5 x10^4 TCID50) was observed. Both higher dose groups (MV-CHIK 0.25 mL = 7.5 x10^4 TCID50; 1 mL = 3 x10^5 TCID50) demonstrated higher GMTs of 48 (LOG10 SD 0.466) and 45.7 (LOG10 SD 0.579).

In the present phase II study, the sample size of 60 subjects in the MV-CHIK dose group vs. 10 subjects in the corresponding control group within each dose group A-D will allow for a detection of a GMT of 15.4 (MV-CHIK) vs. 7.3 (placebo) with a LOG10 SD of 0.6 vs. 0.26 and statistical power of 80% (two-sided alpha=5%, unequal-variance t-test). Between dose groups, the sample size of 60 subjects per group will allow for a comparison of a GMT of 45.7 vs. 22.4 (LOG10 SD 0.6 for both groups) with a statistical power of 80% (two-sided alpha=5%, equal-variance t-test).

Since the magnitude of GMTs and LG10 DS in this assessment is comparable to the observed results in study MV-CHIK-101, and the statistical methodology applied in the current study has a higher statistical power than pairwise t-tests, the chosen sample size seems adequate.

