2.3 Treatment Groups

For tables the groups M1 and M2 are not stratified by country (Austria, Germany):

- M1 of Austria (low dose) and M1 of Germany (high dose) are summarized in one group M1
- M2 of Austria (low dose) and M2 of Germany (high dose) are summarized in one group M2

Following treatment groups will be used in the analysis:

1. Group CV1: control vaccine on Day 0 and 28

SAP (MV-CHIK-202, FINAL 3.0, 09-May-2018) Page 15 of 47 Based on: STAT03_A Statistical Analysis Plan Version 5.0, Effective Date 16-Dec-2016 Confidential and intellectual property of Assign DMB. No part of this document or its contents may be duplicated, referenced, published or otherwise disclosed in any form or by any means without prior written consent of Assign DMB.

- 2. Group CV2: control vaccine on Day 28 and 196
- 3. Group A: MV-CHIK low dose on Day 0 and 28
- 4. Group B: MV-CHIK low dose Day 28 and 196
- 5. Group C: MV-CHIK high dose on Day 0 and 28
- 6. Group D: MV-CHIK high dose Day 28 and 196
- 7. Group M1: MV-CHIK on Day 0 and 28
- 8. Group M2: MV-CHIK on Day 168 and 196

Further, tables will show one total column for

- 9. all MV-CHIK serum groups (i.e. total of A, B, C, D, M1 and M2)
- 10. all control vaccines (i.e. total of CV1 and CV2)

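### For chikungunya titres the SAP splits 40 randomised controls into two ANOVA levels of 20, so each vaccine-versus-control ratio uses half of them, and protocol 13.4 illustrates a 60 vs 10 contrast that the SAP never makes

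*SAP*

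**What the plan says.** Protocol 6.3 randomises ten control-vaccine subjects within each of groups A to D (for example, "Group A: MV-CHIK low : control-vaccine = 60 : 10"), 40 in all. Protocol 13.4 reports no formal sample size calculation, but judges the numbers by a comparison of "60 subjects in the MV-CHIK dose group vs. 10 subjects in the corresponding control group within each dose group A-D". The stated target is "detection of a GMT of 15.4 (MV-CHIK) vs. 7.3 (placebo", with log10 "SD of 0.6 vs. 0.26 and statistical power of 80" percent, by a "two-sided alpha=5%, unequal-variance t-test". It adds that the planned method is more powerful than pairwise t-tests.

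SAP 2.3 regroups the controls by schedule: CV1 (Days 0 and 28, from A and C) and CV2 (Days 28 and 196, from B and D), 20 each as planned. SAP 2.7.1 "will compare the PRNT₅₀ antibody geometric mean titer (GMT) on Day 56 between the treatment groups (CV1, CV2, A, B, C, D, M1, M2", and SAP 2.7.2 uses the same eight levels for PRNT and ELISA titres by visit and for T cells. A pooled control appears only as a table column: "all control vaccines (i.e. total of CV1 and CV2".

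On testing, SAP 2.7 states "The significance level will be 0.05. All p-values will be two-sided" and adjusts pairwise comparisons by Tukey-Kramer. SAP 2.7.1 promises pairwise comparison only among the MV-CHIK groups. Protocol 13.1 lists A vs B, C vs D and M1 vs M2.

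**The concern.** The control in the sizing (10), the control in the model (20) and the control available (40) are three different things. For an anti-chikungunya endpoint, CV1 and CV2 differ only in how much control vaccine has been given and when. Neither contains a chikungunya antigen, and no stated objective or endpoint compares the two on chikungunya titre. All 40 come from the same concurrent, blinded randomisation of A to D, so together they are a valid randomised comparator for each of A, B, C and D.

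At stake is the precision of every vaccine-to-control GMT ratio, and whether 13.4 describes a comparison that will be made.

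**Working it through.** **Inputs.** Protocol 13.4: GMT 15.4 vs 7.3; log10 SD 0.6 (MV-CHIK) and 0.26 (control); two-sided 5%. Protocol 6.3: 60 vaccinees per group, 40 controls, M1 and M2 of 20 each; total 320. Assumption: at Day 56, SD is 0.6 in A to D and M1, and 0.26 in the controls and in M2, which has had no MV-CHIK by then. No dropout.

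**Step 1: the plan's own figure.** Difference = log10(15.4/7.3) = 0.324. Welch standard error for 60 vs 10 = √(0.36/60 + 0.0676/10) = 0.113, with 28.6 Satterthwaite degrees of freedom. Power by noncentral t is 79.2%, so the stated 80% is reproduced.

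**Step 2: the same test with more controls.**
- 60 vs 20: standard error 0.0969, power 91.0%.
- 60 vs 40: standard error 0.0877, power 95.5%.

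**Step 3: interval width in the planned ANOVA.** The half-width on the log10 scale is critical value × residual SD × √(1/n₁ + 1/n₂).
- Split: √(1/60 + 1/20) = 0.258.
- Pooled: √(1/60 + 1/40) = 0.204.
- Reduction: 1 − 0.204/0.258 = 21%. It is 23% if the Tukey critical value also falls from 3.052 (8 levels) to 2.968 (7 levels). With unequal variances it is about 9% (1 − 0.0877/0.0969).

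**Step 4: power in the planned ANOVA.** The pooled error variance is dominated by the vaccine groups.
- Split: [4·59·0.36 + 2·19·0.0676 + 19·0.36 + 19·0.0676]/312 = 0.3066, residual SD 0.554. The model's standard error is 0.554 × 0.258 = 0.143, although the true one is 0.097.
- Pooled: residual SD 0.553, model standard error 0.553 × 0.204 = 0.113.

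Power is approximately Φ[(0.324 − critical value × model standard error)/true standard error].
- Tukey-Kramer, split: (0.324 − 3.052 × 0.143)/0.0969 = −1.16, giving 12.4% (12.8% simulated).
- Tukey-Kramer, pooled: (0.324 − 2.968 × 0.113)/0.0877 = −0.12, giving 45.1% (45.4% simulated).
- Unadjusted, simulated: 67.3% split, 87.7% pooled.

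**Step 5: other SD assumptions, Tukey-Kramer over all levels.**

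| Assumption | Split | Pooled |
|---|---|---|
| M2 SD 0.6 | 10.4% | 41.1% |
| SD 0.6 in every group | 17.1% | 37.6% |
| Noncentral t with the mixed residual SD | 21.9% | 46.3% |

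**Step 6: larger effects, split controls, Tukey-Kramer over all levels.** The range runs from SD 0.6 everywhere to the exposure-based SDs.
- GMT 25: 65% to 84%.
- GMT 35: 91% to over 99%.
- GMT 45.7: at least 98%.

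**The case against.** The strongest reply is that the plan names no vaccine-versus-control test. SAP 2.7.1 and protocol 13.1 limit pairwise comparison to MV-CHIK groups, and for those contrasts pooling adds no group data; it only lowers the critical value slightly. This stands. It means the Tukey-Kramer figures hold only if that family extends to the control levels. It does not remove the point: SAP 2.7.1 includes CV1 and CV2 among the groups compared, and 13.4 rests on vaccine versus control.

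A reader might infer that the split itself cuts the planned analysis to 13% power. The documents do not support that. With the same split, the unadjusted ANOVA has 67% and the Welch test 91%, so Tukey-Kramer and the pooled variance do most of the damage. On the protocol's own test, 20 controls do better than the 10 it was sized on.

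The effect is also the smallest one sized for. Phase 1 GMTs at the two higher doses were 48 and 45.7 after one dose (protocol 13.4), and protocol 2.4 reports a clear boost from a second. Groups A and C have had two doses by Day 56. This stands: the power gain matters for weak responses, though the precision gain remains at any effect size.

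Finally, CV1 and CV2 are schedule-matched controls. They differ in control-vaccine doses received: one vs none at Day 28, two vs one at Day 56. Phase 1 controls had a GMT of 7.3 although negatives were set to 5, so background was not nil. Matching is defensible, and losing it in the model is a real but small cost.

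**Conclusion.** The concern holds as a matter of efficiency and of alignment between sizing and analysis. Splitting the controls for chikungunya endpoints answers no stated question and widens each vaccine-to-control interval: pooling would narrow it by about 21% in the planned pooled-variance model, and about 9% with unequal variances. At the sized effect the gain is 91% to 96% (Welch), 67% to 88% (unadjusted ANOVA), or about 13% to 45% (Tukey-Kramer over all levels; 10–22% to 38–46% under other SD assumptions). These figures assume planned numbers and the protocol's SDs.

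Pooling does not bring the Tukey-Kramer analysis back to 80%, and it adds little power at GMTs of about 35 or above. It would be wrong to conclude that the split makes the trial underpowered, or that pooling alone repairs the vaccine-versus-control test. The claim in 13.4 that the planned method beats pairwise t-tests is not borne out for vaccine versus control at these SDs: with 20 controls, Welch gives 91% and the unadjusted ANOVA 67%.

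**What to change.** - In SAP 2.7.1 and 2.7.2, for chikungunya PRNT50 and chikungunya ELISA, use one control level holding all A to D controls (planned n = 40). Alternatively, keep eight levels and pre-specify a contrast against the CV1/CV2 average. With equal numbers this is the same estimate; at the 8-level Tukey value its power is about 41%.
- State whether vaccine versus control is tested, and with what multiplicity adjustment.
- For T cells, pool whatever controls were enrolled in Vienna. Sampling is confined to those sites (protocol 8.3.3, SAP 6.5), so 40 will not be available.
- Show CV1 and CV2 separately as descriptive columns, and keep them separate for measles ELISA and safety, where the doses received matter.
- Restate the vaccine-versus-control figure in protocol 13.4 for 60 vs 40, using the test actually planned.

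The cost is SAP wording and one recoded factor, with no extra subjects, visits or samples. The schedule-matched comparison on chikungunya titres becomes descriptive only. SAP 2.2.1 scheduled the preliminary analysis for August 2017, and SAP 10.1 marks the primary ANOVA table for it, while SAP version 3.0 is dated May 2018. Any preliminary results already produced with split controls should therefore be reported alongside the pooled analysis, and the change recorded with its date.

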## 4 STUDY PLAN

### 4.1 Study Endpoints

#### 4.1.1 Primary endpoint

- Immunogenicity on day 56 confirmed by the presence of functional anti-chikungunya antibodies as determined by the plaque reduction neutralization test (PRNT50)

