### 13.1 Immunogenicity Analysis

The primary immunogenicity analysis will compare the anti-chikungunya PRNT50 antibody geometric mean titer (GMT) 28 days after one or two immunizations in the Per Protocol (PP) analysis population between the treatment groups. GMTs and GMT ratios will be estimated by applying an analysis of variance including the factor vaccination group. This will be done using log-10 transformed data and taking the anti-log of the resulting point estimates for the least squares means, least squares means differences and the corresponding 2-sided 95% CIs. P-values will also be provided to compare GMTs for the MV-CHIK groups (pairwise comparisons adjusted for multiple comparisons according to Tukey-Kramer; groups A vs. B, C vs. D, M1 vs. M2), e.g. 28 days after the 2nd MV-CHIK dose, etc. Likewise, SCRs will also be compared between groups. Seroconversion will be defined as anti-Chikungunya PRNT50 titers  $\geq 10$ .

Measles ELISA titers will be analyzed as described above. In addition, the effect of pre-existing anti-measles immunity will be assessed: The CHIKV PRNT50 titers 28 days after first vaccination, between the four baseline measles titer groups, defined by baseline percentiles

(25%, 25-50%, 50-75%, 75-100%), will be compared. No stratification by dose groups is intended.

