1.3 Endpoints

1.3.1 Primary Endpoint

Immunogenicity on Day 56 confirmed by the presence of functional anti-chikungunya antibodies as determined by the plaque reduction neutralization test (PRNT₅₀)

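### At Day 56 group M2 has had no MV-CHIK, yet the SAP counts it as an MV-CHIK group in the pairwise set and in the pooled MV-CHIK column

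*SAP*

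**What the plan says.** Both documents place the primary endpoint at Day 56. Protocol 4.1.1 reads "Immunogenicity on day 56 confirmed by the presence of functional anti-chikungunya antibodies as determined by the plaque reduction neutralization test", and SAP 1.3.1 has "Immunogenicity on Day 56 confirmed by the presence of functional anti-chikungunya antibodies". Protocol 13.1 describes the primary analysis by dose, as the "geometric mean titer (GMT) 28 days after one or two immunizations in the Per Protocol (PP) analysis population between the treatment groups". For pairwise p-values it names "groups A vs. B, C vs. D, M1 vs. M2), e.g. 28 days after the 2nd MV-CHIK dose".

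SAP 2.7.1 compares the primary titer as "GMT) on Day 56 between the treatment groups (CV1, CV2, A, B, C, D, M1, M2" and adds that "GMTs for the MV-CHIK groups will be compared pairwise". It does not say which groups are meant. The only definition is item 9 of SAP 2.3, which sets up a total column for "all MV-CHIK serum groups (i.e. total of A, B, C, D, M1 and M2", with no restriction by visit. The tables in SAP 6.1 and 6.2 give PRNT50 and ELISA GMTs and seroconversion rates by treatment group and overall.

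The schedule (Protocol 1.1 and 6.1; SAP 1.2) gives M2 control vaccine on Day -28, placebo on Days 0 and 28, and MV-CHIK on Days 168 and 196. Groups B and D get placebo on Day 0 and their first MV-CHIK on Day 28.

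**The concern.** A subject who has not yet had MV-CHIK can say nothing about the response to it. At Day 56 that is all of M2. At Day 28 it is B, D and M2, because Protocol 8.2.3 describes the blood draw ahead of that day's injection.

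Two outputs are affected. Any Day 56 contrast with M2 appears among comparisons of MV-CHIK regimens, although one side has had no MV-CHIK. M1 against M2 at that visit looks like a comparison of two schedules but is two doses against none. Second, the pooled MV-CHIK figures mix dosed and undosed subjects, and so understate the response of vaccine recipients. This applies with most force to the Preliminary Analysis. Its immunogenicity samples stop at Day 56 (SAP 6.2.1), so M2 contributes only undosed data there, and its stated purpose is to inform further development.

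**Working it through.** **Inputs.** Planned numbers (Protocol 6.3): 60 MV-CHIK subjects in each of A, B, C and D, and 20 each in M1 and M2, so 4 × 60 + 20 + 20 = 280 in the pooled column. Titers (Protocol 13.4): Phase 1 Day 28 GMT of 45.7 in the highest-dose cohort and 7.3 in the group it calls placebo. SAP 6 substitutes 5 for a PRNT50 below 10, so 5 is the floor for undosed subjects.

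**The plan's own figures.** Protocol 13.4 states 80% power for two comparisons.
- GMT 45.7 vs 22.4, 60 per group, log10 SD 0.6: difference log10(45.7/22.4) = 0.3097, SE = 0.6 × √(2/60) = 0.1095. Power is 80.7% by the normal approximation and 80.1% by the noncentral t.
- GMT 15.4 vs 7.3, 60 vs 10, SDs 0.6 and 0.26, unequal variances: 79.2%, with 28.6 degrees of freedom.

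Both reproduce, so the titers and SDs are used as the plan uses them.

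**MV-CHIK doses received before each blood draw**

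| Group | n | Day 28 | Day 56 |
|---|---|---|---|
| A, C | 120 | 1 | 2 |
| B, D | 120 | 0 | 1 |
| M1 | 20 | 1 | 2 |
| M2 | 20 | 0 | 0 |

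Undosed share of the pooled column: 20/280 = 7.1% at Day 56, and (120 + 20)/280 = 50% at Day 28.

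**Pairs.** Six MV-CHIK groups give 6 × 5/2 = 15 pairs. M2 is in 5 of them.

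**Effect on the other ten pairs.** M2 is its own level in the ANOVA, so the estimates do not move. Only the pooled residual SD and the Tukey critical value change. The 95% half-width for 60 vs 60 on the log10 scale is (q/√2) × s × √(2/60). Assume SD 0.6 in the dosed groups and 0.26 in M2 and the controls.
- All eight groups: 3.052 × 0.554 × 0.1826 = 0.308, or 2.035-fold. Without M2: 2.969 × 0.568 × 0.1826 = 0.308, or 2.031-fold.
- Six MV-CHIK groups only: 2.020-fold. Without M2: 2.000-fold.

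The change is about 1% at most.

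**Pooled GMT.** log10(pooled) = (n_dosed × log10 G_dosed + n_undosed × log10 G_undosed)/280.
- Day 56: (260 × 1.6599 + 20 × 0.8633)/280 = 1.6030, so 40.1 instead of 45.7, or 12% low. With undosed at 5 it is 39.0, or 15% low.
- Day 56 over assumed dosed GMTs from 22.4 to 200, undosed at 5 or 7.3: 8% to 23% low.
- Day 28: (140 × 1.6599 + 140 × 0.8633)/280 = 1.2616, so 18.3 instead of 45.7. With undosed at 5 it is 15.1.

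**Pooled seroconversion.** Rate = (n_dosed × p_dosed + n_undosed × p_undosed)/280. With p_undosed = 0 and p_dosed = 1, the ceiling is 260/280 = 92.9% at Day 56 and 140/280 = 50% at Day 28. A true 90% among dosed subjects would show at Day 56 as 260 × 0.9/280 = 83.6%.

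**The case against.** Much of the case on the other side stands.

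- A reader might infer that the SAP moved the primary time point from a dose-based to a calendar-based one. The documents do not support that. The protocol's own primary endpoint is Day 56, and for A, B, C, D and M1 that day is 28 days after one or two MV-CHIK doses. Only M2 fails to fit the description in Protocol 13.1, which itself lists M1 vs M2 among the MV-CHIK comparisons. Part of the ambiguity therefore starts in the protocol.
- A reader might also infer that the primary comparisons in general are diluted. They are not. M2 is not merged into another arm, and the ten contrasts without it are essentially unchanged. The five with M2 are mislabelled rather than diluted; M1 vs M2 at Day 56 is informative if read as vaccine against no MV-CHIK.
- M2's real response is not lost. SAP 2.7.2 has a by-visit ANOVA that covers M2 at Days 196 and 224, and a separate comparison of M1 at Day 56 with M2 at Day 224. M2 serves a secondary endpoint, so its dose-aligned result belongs there.
- The pooled column is descriptive. No immunogenicity test uses it, each group is shown beside it, and SAP 2.3 prints M2's vaccination days. Even without M2 it mixes two dose levels and different numbers of doses.
- The size rests on one Phase 1 GMT, from one dose in the highest-dose cohort, applied to every dosed subject. The larger figures belong to Day 28, a secondary visit.

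None of this removes the pooling rule. As written, it reports undosed subjects under an MV-CHIK heading, and a schedule in the group definitions does not correct the number in the column.

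**Conclusion.** The point holds in a limited form. Followed as written, the SAP treats M2 as an MV-CHIK group at Day 56 when it has had none, which mislabels 5 of 15 pairwise comparisons and lowers the descriptive pooled figures. The undosed shares, 7.1% at Day 56 and 50% at Day 28, follow from the planned numbers and the schedule alone. The size of the understatement depends on assumed titers: about 8% to 23% in GMT at Day 56, and 18.3 instead of 45.7 at Day 28 in the Phase 1 illustration. The seroconversion ceilings of 92.9% and 50% assume that no undosed subject reaches titer 10. All figures use planned numbers with no dropout. The dosed GMTs of 100 and 200 within the range and the 90% seroconversion rate are illustrative. Estimates among A, B, C, D and M1 are sound, and the primary time point agrees between the documents.

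**What to change.** In SAP 2.7.1, name the groups in the Day 56 pairwise set as A, B, C, D and M1. Show M2 at that visit as a not-yet-vaccinated reference (control vaccine plus placebo). Keep the M1 Day 56 vs M2 Day 224 comparison in SAP 2.7.2 as the comparison of schedules.

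In SAP 2.3, limit the pooled MV-CHIK column of the immunogenicity tables, at each post-baseline visit, to groups that received MV-CHIK before that visit, split by one or two doses. This leaves out M2 at Day 56 and B, D and M2 at Day 28. The same rule leaves out M2 at Day 168, when only M1 and M2 are sampled and M2 is about to get its first dose.

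The cost is SAP wording and table programming. No new data are needed, and the by-group columns do not change.

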### **8.2 Treatment Procedures**

#### **8.2.1 Study day -28 ( $\pm 5$ days) /Visit 0 (or day 0 /Visit 1 for group A-D)**

Subjects, who do not have to be in a fasted state, are requested to return within 7 days after screening visit, at the study site where inclusion and exclusion criteria will be checked once again and their medical history and concomitant medication will be updated, if necessary. A urine pregnancy test will be performed in women of childbearing potential. Symptom-directed physical exam, system-based assessment (only if necessary according to symptom-directed physical exam) and vital signs (systolic and diastolic blood pressure, pulse and body temperature) will be recorded. In addition, the subjects will be asked if they experience any kind of arthralgia. Blood samples for baseline immunogenicity 1 and measles antibody titer will be drawn from an appropriate forearm or cubital vein. All study sites except the two sites in Vienna will collect serum samples for cross neutralization and passive transfer analyses (immunogenicity 2).

Then subjects will be randomized and will receive their 1st vaccination according to the assigned treatment group.

- Group A, B, C and D will perform Visit 0 = Visit 1 procedures on one day (study day 0, just one visit).
- Group M1 and M2 will perform Visit 0 and Visit 1 separated on two days, 28 days apart (study day -28 and study day 0, two visits)

All subjects will be observed for 1 hour after each vaccination before discharge from study site. One hour after vaccination local tolerability and adverse events, if applicable, will be recorded.

Subjects will be discharged after the dispense and the instructions for the use of the subject diaries took place (subjects are asked to report any adverse events in the diary for 7 days after vaccination). Only if the investigating physician considers the situation to be safe for the subjects, they will be allowed to leave the department and will be asked to return to study site after 28 days ( $\pm$  5 days).

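### The primary Day 56 PRNT50 model omits the baseline titre measured in every subject; the cost is a modest, uncertain loss of precision, not bias

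*SAP*

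**What the plan says.** SAP 2.7.1 compares Day 56 PRNT50 titres across eight groups (CV1, CV2, A, B, C, D, M1, M2) and says "GMTs and GMT ratios will be estimated with including the factor vaccination group". Protocol 13.1 agrees: "GMTs and GMT ratios will be estimated by applying an analysis of variance including the factor vaccination group". The outcome is log10-transformed. Neither document puts a covariate in the primary model.

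The candidate covariates are already collected. At the first treatment visit, before randomisation and injection, Protocol 8.2.1 says "Blood samples for baseline immunogenicity 1 and measles antibody titer will be drawn". That visit is Day 0 for A-D and Day -28 for M1 and M2; Protocol 8.3.1 (Table 3) and 10.1 confirm the schedule. Baseline measles titre is used only in separate secondary analyses by quartile (SAP 2.7.2), which leave out treatment group. Baseline PRNT50 is summarised and compared between groups by visit, but is not used as a covariate.

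**The concern.** Any between-subject variation in Day 56 titre that the pre-injection titre could explain stays in the error term, and widens every GMT-ratio interval. This matters somewhat because the trial has no formal sample size calculation, several groups are small (20 each in CV1, CV2, M1 and M2), and the results are meant to guide the dose and schedule for Phase 3.

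Whether there is anything to explain depends on whether baseline PRNT50 varies. The documents give one hint. Protocol 13.4 reports a Phase 1 GMT of 7.3 with log10 SD 0.254 "at day 28 in the placebo group". Protocol 2.4 says titres below 10 were entered as 5, so an entirely negative group would show GMT 5 and SD 0. Protocol 7.3 excludes prior chikungunya vaccination but lists no exclusion for prior infection or baseline seropositivity.

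**Working it through.** **Inputs.** SAP 2.7: "The significance level will be 0.05. All p-values will be two-sided". Protocol 13.4: "Between dose groups, the sample size of 60 subjects per group will allow for a comparison of a GMT of 45.7 vs. 22.4", with "SD 0.6 for both groups) with a statistical power of 80% (two-sided alpha=5%, equal-variance t-test". Dropout is taken as zero.

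**Step 1: reproduce the plan's figure.**
- Difference on the log10 scale: log10(45.7/22.4) = 0.310.
- Standard error: 0.6 × √(2/60) = 0.1095.
- Noncentrality: 0.310/0.1095 = 2.83.
- Noncentral t with 118 df: power 80.1%. The stated 80% is reproduced, and it assumes no covariate.

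**Step 2: add a baseline covariate.** Let ρ be the within-group correlation between baseline and Day 56 log10 PRNT50. The residual SD becomes 0.6 × √(1 − ρ²), with one degree of freedom lost. The documents give no ρ, so a range is shown. The equivalent n per group is 60/(1 − ρ²). The interval factor is 10 to the power of (t critical value × standard error).

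| ρ | Reduction in SE | Power | Equivalent n per group | 95% interval factor for the GMT ratio |
|---|---|---|---|---|
| 0 | 0 | 80.1% | 60 | 1.65 |
| 0.10 | 0.5% | 80.4% | 61 | 1.64 |
| 0.16 | 1.3% | 81.1% | 62 | 1.64 |
| 0.26 | 3.4% | 82.7% | 64 | 1.62 |
| 0.30 | 4.6% | 83.6% | 66 | 1.61 |
| 0.42 | 9.3% | 87.1% | 73 | 1.57 |

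**Step 3: which ρ is plausible?**
- *Ceiling.* If all the Phase 1 control spread is stable within a subject and adds fully to the vaccine response on the log scale, ρ = 0.254/0.6 = 0.42. Assay noise, or incomplete carry-over, lowers it. Using the Phase 1 MV-CHIK SDs (0.466 to 0.579) in place of 0.6 raises the ratio to 0.44-0.55, but unadjusted power is then already 83-95% and the gain is still no more than about 7 points.
- *Middle.* Assume instead that background adds on the titre scale: lognormal background, values below 10 coded 5, matched to GMT 7.3 and SD 0.254, with the post-vaccination titres matched to SD 0.6. Then ρ is about 0.16 at GMT 45.7 and about 0.25-0.26 at GMT 22.4. This still assumes no assay noise.
- *Floor.* If nearly all baselines are below 10, the covariate is close to constant and the gain is close to zero.
- *Is a varying baseline credible?* With a floor of 5, the log-mean excess is log10(7.3/5) = 0.164. At least 0.164²/(0.164² + 0.254²) ≈ 29% of that control arm must have read above the negative code. That is a Day 28 figure, not a baseline.

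**Step 4: chance imbalance.** A one-SD chance difference in baseline shifts the log10 contrast by ρ × 0.6 × √(2/60). At ρ = 0.3 this is 0.033, a factor of 1.08 on the GMT ratio. The unadjusted interval (factor 1.65) already contains this source of variation, so it is the precision loss of Step 2 seen from another side, not an addition to it.

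**The case against.** The strongest counter-case is that the gain is undocumented and may be trivial. No Day 0 PRNT50 value appears in the text. The 7.3/0.254 figures come from one arm of a 42-subject, four-arm study, after an injection; Protocol 2.4 says that the control group received Priorix. For measles titre the evidence points the other way: Protocol 2.4 reports that Phase 1 subjects with low, medium and high baseline titres responded alike. All of this stands. It limits the size of the point, but not the logic of pre-specifying a cheap adjustment.

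Two stronger readings are tempting, and the documents support neither. A reader might infer that chance imbalance in the small groups biases the primary contrast. It does not: assignment is randomised, the unadjusted estimate is unbiased, and its interval covers such imbalance. A reader might also infer a gain of 10 points or more from a conventional correlation of 0.5. At the plan's SD that exceeds the ceiling obtainable from the Phase 1 figures, and nothing in the documents supports it.

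Power under multiplicity is a separate matter. SAP 2.7 says "Pairwise comparisons for multiple comparisons will be adjusted according to Tukey-Kramer". If that family is all eight groups, power for the same contrast is about 41% without a covariate; for six groups it is about 48%. That loss comes from the multiplicity adjustment, not the missing covariate.

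Timing and form also deserve weight. Group-only ANOVA is the protocol's model, the SAP lists the primary ANOVA for both the preliminary and the final analysis (10.1, Table 3.1.3), and the preliminary analysis was set for August 2017, before this SAP version of May 2018. CV1, CV2 and M2 have received no MV-CHIK by Day 56, so their baseline slope may differ from that of the vaccinated groups. Both points are met by confining the change to the final analysis, keeping the unadjusted model in the report, and checking the slope.

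**Conclusion.** The concern holds as a precision point of modest and uncertain size. Both documents specify a group-only model, and both titres are scheduled in every subject before the first injection. For the plan's own 60 vs 60 contrast, leaving out baseline costs between almost nothing and about 7 points of power (80% to at most 87%). A range of 1 to 4 points corresponds to correlations of 0.16 to 0.3. This rests on an assumed correlation, SD 0.6, no dropout, and the unadjusted two-sided 5% test used in Protocol 13.4. The upper end further requires the Phase 1 control spread to be wholly stable and additive on the log scale. Validity of the planned analysis is not in question. Adjustment is worth making because it uses existing data at almost no cost.

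**What to change.** **SAP 2.7.1, final analysis.** Fit log10 Day 56 PRNT50 on treatment group plus log10 PRNT50 from before the first injection: Day 0 for A-D and CV1/CV2, Day -28 for M1 and M2. Day 0 should not serve as baseline in M1 and M2, because it follows Priorix and would adjust away part of its effect. Log10 measles titre from the same sample may be added, though Phase 1 suggests little gain.

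**Safeguards.** Keep the protocol's unadjusted ANOVA as a reported sensitivity analysis. Check whether the baseline slope differs between groups that have received MV-CHIK by Day 56 and those that have not (CV1, CV2, M2). Record the departure from Protocol 13.1 in SAP 2.17, which at present says that no change to the planned analysis is intended.

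**If extended to SAP 2.7.2.** Apply it only to visits after the first injection. Leave out the Day 0 and Day -28 models, where outcome and covariate are the same measurement for some or all groups. For T cells, restrict it to the final analysis: the preliminary one covers Day 56 only (SAP 6.5.1), whereas Day 0 values are scheduled for the final one (6.5.2).

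**Cost.** One or two degrees of freedom out of 320 − 8 = 312, one extra model, and SAP wording. No new data are needed.
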